PROTOCOL TITLE 'Incidence of Cervical Cancer in HPV-positive Women with Low-grade Cytological Abnormalities'

Protocol ID	2025-03
Short title	Incidence of Cervical Cancer in HPV-positive Women with Low-grade Cytological Abnormalities
Version	2.3
Date	November 2025

TABLE OF CONTENTS

1. INTRODUCTION AND RATIONALE	7
2. OBJECTIVES	8
3. STUDY DESIGN	9
4. STUDY POPULATION	9
4.1 Population (base)	9
4.2 Inclusion criteria	9
4.3 Exclusion criteria	9
5. METHODS	10
5.1 Study parameters/endpoints	10
5.1.1 Main study parameter/endpoint	10
5.1.2 Secondary study parameters/endpoints	10
5.1.3 Other study parameters	10
6. STATISTICAL ANALYSIS	11
6.1 Primary study parameter(s)	11
6.2 Secondary study parameter(s)	11
6.3 Other study parameters	11
7. ETHICAL CONSIDERATIONS	13
7.1 Regulation statement	13
7.2 Recruitment and consent	13
8. ADMINISTRATIVE ASPECTS, MONITORING AND PUBLICATION	14
8.1 Handling and storage of data and documents	14
8.2 Amendments	14
8.3 Public disclosure and publication policy	14
9. REFERENCES	15

LIST OF ABBREVIATIONS AND RELEVANT DEFINITIONS

AGC: Atypical Glandular Cells of Endocervical Origin

ASC-US: Atypical Squamous Cells of Undetermined Significance

CIN: Cervical Intraepithelial Neoplasia

HPV: Human Papillomavirus

IQR: Interquartile Range

LSIL: Low-grade Squamous Intraepithelial Lesion

NILM: Negative for Intraepithelial Lesion or Malignancy

PALGA: Dutch nationwide pathology databank

SD: Standard Deviation

SUMMARY

Rationale:

Since 2017, the Dutch cervical cancer screening program has adopted human papillomavirus (HPV) testing with referral for colposcopy in all HPV-positive women with cytological abnormalities. However, most low-grade abnormalities — atypical squamous cells of undetermined significance (ASC-US), atypical glandular cells of endocervical origin (AGC), and low-grade squamous intraepithelial lesions (LSIL) — regress spontaneously, which may result in overdiagnosis, overtreatment, and unnecessary pressure on the healthcare system. To evaluate whether follow-up intensity can be safely reduced, it is important to assess the actual cancer risk in this subgroup and compare it with the risk in women with stable negative for intraepithelial lesion or malignancy (NILM) cytology after one year, who are currently returned to the screening program.

Objective:

- Primary objective: To determine the five-year incidence of histologically confirmed cervical cancer in HPV-positive women with low-grade cytological abnormalities detected through the Dutch cervical cancer screening program.
- Secondary objectives:
 - To assess time to cervical cancer diagnosis, all-cause mortality, the type of examination at which the diagnosis was established, and the histological characteristics of the carcinoma (subtype) in this population, within five years after enrollment.
 - To assess cervical cancer risk stratified by histological diagnosis within three months of baseline abnormal cytology (\leq cervical intraepithelial neoplasia (CIN) I vs CIN 2+) and, for the \leq CIN I group, further stratified by cytology at 12-month follow-up (no or nondiagnostic cytology, \leq LSIL, HSIL+).
 - To perform a sub-analysis of women with a history of abnormal cytology or histology and assess their five-year cervical cancer risk after enrollement.
 - To evaluate the incidence of cervical cancer in women with stable NILM cytology after one year and compare it with the five-year incidence in women with low-grade cytological abnormalities.

Study design:

Retrospective cohort study based on routinely collected data from the Dutch population-based cervical cancer screening program.

Study population:

Women who participated in the cervical cancer screening program in the Netherlands between January 2017 and December 2018, who:

- Tested HPV-positive with cytology results categorized as ASC-US, AGC, or LSIL according to the Bethesda system, or
- Had stable NILM cytology after one year.

Main study parameters/endpoints:

Primary endpoint: Incidence of histologically confirmed cervical cancer within the five-year screening interval.

Secondary endpoints:

- Time to diagnosis of cervical cancer, all-cause mortality, the type of examination at which the diagnosis was established, and the histological characteristics of carcinoma (subtype), within five years after enrollment.
- Cervical cancer incidence in women with a history of abnormal cytology or histology.
- Cervical cancer risk stratified by histological diagnosis within three months of baseline abnormal cytology (\leq CIN 1 vs CIN 2+) and, for the \leq CIN 1 group, further stratified by cytology at 12-month follow-up (no or nondiagnostic cytology, \leq LSIL, HSIL +). With a follow-up period of five years and three months after enrollment.
- Cervical cancer incidence in women with stable NILM cytology after one year.

Nature and extent of the burden and risks associated with participation, benefit and group relatedness:

As this is a retrospective cohort study using existing screening data, no direct burden, risks, or interventions are associated with study participation. The potential benefit lies at the population level: results may provide evidence to optimize follow-up strategies for HPV-positive women with low-grade cytological abnormalities or persistent NILM results, and for those with relevant medical history, thereby reducing unnecessary procedures while maintaining safe cancer detection.

1. INTRODUCTION AND RATIONALE

Cervical cancer is the fourth most common cancer among women worldwide and remains a leading cause of cancer-related mortality.[1] Prevention is largely possible through organized screening programs. These typically involve the collection of cervical samples to test for the presence of human papillomavirus HPV and to detect cytological abnormalities suggestive of (pre)cancerous lesions.[2,3] Implementation of such screening programs has been associated with a reduction in the incidence of cervical cancer.[4,5]

In the Netherlands, the national cervical cancer screening program invites women aged 30 to 60 every five years.[6] Since 2017, the Dutch program has shifted from a cytology-based to primary HPV based screening, according to international guidelines.[6–8] This shift aims to improve early detection of high-grade lesions and reduce cervical cancer incidence, as over 90% of women with cervical cancer are HPV-positive.[9] Women who test HPV-positive undergo follow-up cytology, and those with abnormal cytology—regardless of grade— are referred for colposcopy.

However, a considerable proportion of HPV-positive women present with low-grade cytological abnormalities, which often regress spontaneously without progressing to cervical cancer [10–12] Previous studies have shown that the long-term risk of cervical cancer in these women is relatively low. Nonetheless, referring them for colposcopy places a burden on healthcare resources, contributes to patient anxiety, and may lead to overtreatment.[13] In the context of rising healthcare costs and increasing pressure on the medical system, it is increasingly relevant to assess whether follow-up intensity for this subgroup can be safely reduced.

To date, the long-term risk of cervical cancer in HPV-positive women with low-grade cytological abnormalities has not been thoroughly evaluated. Given that eligible women are invited for screening every five years, it is crucial to assess whether these baseline abnormalities may progress to cervical cancer within that interval. Therefore, this study investigates the five-year incidence of cervical cancer among HPV-positive women with low-grade cervical abnormalities participating in the Dutch cervical cancer screening program.

2. OBJECTIVES

Primary Objective:

To determine the five-year incidence of histologically confirmed cervical cancer in HPV-positive women with low-grade cytological abnormalities detected through the Dutch cervical cancer screening program.

Secondary Objectives:

- To assess time to cervical cancer diagnosis, all-cause mortality, type of examination at which the diagnosis was established and the histological characteristics of the carcinoma (subtype) in this population , within five years after enrollment.
- To assess cervical cancer risk stratified by histological diagnosis within three months of baseline abnormal cytology (\leq CIN 1 vs CIN 2+) and, for the \leq CIN 1 group, further stratified by cytology at 12-month follow-up (no or nondiagnostic cytology, \leq LSIL, HSIL +), with a follow-up period of five years and three months after enrollment.
- To perform a sub-analysis of women with a history of abnormal cytology or histology and assess their five-year cervical cancer risk.
- To evaluate the incidence of cervical cancer in women with stable NILM cytology after one year and compare it to the five-year incidence in women with low-grade cytological abnormalities.

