4.3 Exclusion criteria

There are no exclusion criteria.

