5.1.3 Other study parameters

- Baseline characteristics such as age at inclusion.
- Cytology according to the Bethesda system and histology results at baseline and follow-up.
- HPV test results at baseline and follow-up.
- Relevant medical history, including prior abnormal cytology or histology.

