6.2 Secondary study parameter(s)

Secondary study parameters include:

- Time-to-diagnosis of cervical cancer, which will be displayed in a line diagram with time on the y-axis and number of cases on the x-axis.
- All-cause mortality, type of examination at which the diagnosis was established, and histological subtype of cervical cancer, which will be summarized as frequencies and percentages for each relevant group.
- Cervical cancer incidence in women with stable NILM cytology after one-year follow-up, cervical cancer incidence in women with a history of abnormal cytology or histology, and risk stratification by histology within three months of baseline cytology and follow-up cytology at 12 months. For these parameters, cumulative incidence and incidence rates will be calculated.

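### The nested 12-month strata ignore histology from months 3 to 12, so CIN 2 or CIN 3 first found then is counted in the CIN 1-or-less cytology cells

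*Combined protocol and SAP*

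**What the plan says.** The Secondary Objectives in section 2 set the first level: "To assess cervical cancer risk stratified by histological diagnosis within three months of baseline abnormal cytology", with CIN 1 or less against CIN 2 or worse. The CIN 1-or-less group is then "further stratified by cytology at 12-month follow-up (no or nondiagnostic cytology", LSIL or less, HSIL or worse), and this objective runs "with a follow-up period of five years and three months after enrollment". The Summary and section 5.1.2 describe the same two levels. Section 6.2 refers to "risk stratification by histology within three months of baseline cytology and follow-up cytology at 12 months" and gives the whole analysis in one sentence: "For these parameters, cumulative incidence and incidence rates will be calculated".

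Section 5.1.3 lists "Cytology according to the Bethesda system and histology results at baseline and follow-up" among the other parameters, so histology after month 3 will be in the dataset. Section 6.3 plans to tabulate it as counts and percentages. Section 4.3 says "There are no exclusion criteria". No section reclassifies, censors or separately reports women whose CIN 2 or CIN 3 is first found after month 3 and by month 12.

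**The concern.** A nested cell such as *CIN 1 or less, then LSIL or less at 12 months* joins two readings nine months apart and skips the histology between them. Take a hypothetical woman with LSIL at baseline, CIN 1 on biopsy at week 8, CIN 3 on histology at month 7, and NILM at month 12. The rule places her in that cell, beside women in whom nothing above CIN 1 was ever found. If she has no 12-month cytology, she falls in the no-or-nondiagnostic cell, beside women who simply had no follow-up. More than one cell is therefore affected.

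The introduction gives the study's purpose: "it is increasingly relevant to assess whether follow-up intensity for this subgroup can be safely reduced". High-grade lesions found in months 3 to 12 come from the care whose intensity is in question. Folding those women into the low-grade cells hides how many there were and what their later cancer risk was. A reader will naturally take the cell as low-grade disease throughout the first year, which the rule does not ensure.

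**Working it through.** The plan states no sample size, event count or expected risk, so there is no figure of its own to reproduce. The check has three parts.

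**1. Which information each level uses** (sections 2, 5.1.2, 5.1.3, 6.2 and 6.3)

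| Information | Level 1 | Level 2 |
|---|---|---|
| Histology, baseline to month 3 | used | inherited from level 1 |
| Histology, months 3 to 12 | not used | not used |
| Cytology at month 12 | not used | used |

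The months 3 to 12 histology is collected but classifies nobody. With no exclusions and no reclassification rule, women with an interim CIN 2 or CIN 3 remain in the CIN 1-or-less cells.

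**2. Time arithmetic** (inputs: 3, 12 and 63 months; enrollment is taken as the baseline screening date)

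- Stated follow-up: 5 × 12 + 3 = 63 months.
- Share of follow-up elapsed when the second level is read: 12/63 = 19%.
- Length of the unclassified window: 12 − 3 = 9 months, which is 9/60 = 15% of the follow-up after month 3.
- Follow-up left after month 12: 63 − 12 = 51 months.

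**3. Effect on a cell's risk** (illustration on assumed values)

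Let f be the share of a cell with CIN 2 or CIN 3 first found in months 3 to 12, and RR their cancer risk relative to the rest of the cell. Then

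observed risk ÷ risk without these women = (1 − f) + f × RR.

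| f | RR = 0 | RR = 1 | RR = 5 |
|---|---|---|---|
| 1% | 0.99 | 1.00 | 1.04 |
| 5% | 0.95 | 1.00 | 1.20 |
| 10% | 0.90 | 1.00 | 1.40 |
| 15% | 0.85 | 1.00 | 1.60 |

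Suppose the observed risk is 100 per 100,000 (assumed). With RR = 0, removing these women gives 100/0.97 = 103 at f = 3% and 100/0.90 = 111 at f = 10%. With RR = 5, the divisors are 0.97 + 0.15 = 1.12 and 0.90 + 0.50 = 1.40, giving 89 and 71. The documents give neither f nor RR, so the sign and the size both stay open.

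**The case against.** The strongest reply is that nothing is mislabelled. The plan puts the three-month window in the stratum's definition, and risk given month-3 histology and 12-month cytology under usual care is a coherent quantity. For level 1 this stands in full: a status fixed at month 3 is a legitimate label. For the nested cells it stands only formally. They are read at month 12 and omit a more specific finding that is already in hand by then.

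Three stronger readings are tempting, and the documents do not support them.

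- *These cells are the group proposed for less follow-up.* The Summary rationale and section 1 define that group by baseline low-grade cytology; the Summary's paragraph on burden and benefit adds persistent NILM and relevant history. The nested cells are one secondary stratification that may inform the decision.
- *The lesions were removed, so the low risk is due to treatment.* No treatment variable is listed in sections 5.1.2 or 5.1.3. That the lesions were managed is an inference.
- *The distortion is very large.* One could assume that 3% to 10% have a later CIN 2 or CIN 3 and that 0.5% to 2% of those would progress to cancer if undetected. This gives 3% × 0.5% = 15 to 10% × 2% = 200 per 100,000. That is a hypothetical averted risk, a quantity the plan does not estimate. It is not an error in the observed figure, and moving women to another row would not recover it.

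A further objection concerns the remedy. Section 5.1.2 leaves the upper histology category open-ended, so it includes cancer. If women were reclassified on any CIN 2-or-worse histology by month 12 while time still ran from enrollment, cancers found in months 3 to 12 would leave the CIN 1-or-less cells by construction, and those cells would look safer than they are. This is correct, and it shapes the fix below.

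Finally, the tabulation in section 6.3 might show some of the later CIN 2 or CIN 3. It specifies neither their timing nor the nested cells, so it does not close the gap.

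**Conclusion.** The point holds for the nested cells of one secondary analysis. As written, women with CIN 1 or less at month 3 and CIN 2 or CIN 3 first found in months 3 to 12 are counted in the CIN 1-or-less cytology cells with women who had no such finding. Level 1 and the primary estimate are not affected.

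The size and direction cannot be determined from the documents. Under the assumptions shown, the observed cell risk lies between 0.85 and 1.60 times the risk without these women (f from 1% to 15%, RR of 0 or 5), and there is no change if RR = 1. The conclusion rests on the stratification rule as written and on the absence of any rule for interim histology, not on these figures. Because the direction is unknown, showing these women separately is more useful than arguing about the bias. It is worth changing before the analysis, since the data are already collected.

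**What to change.** - **Level 1:** keep the month-3 split, with follow-up as planned. Report cancers diagnosed before month 12 here, separately, so that the outcome does not define a level-2 stratum.
- **Level 2, population and time:** take women with CIN 1 or less at month 3 who are alive and free of cervical cancer at month 12. Count time from month 12 to the end of the 63 months. The split by 12-month cytology needs this start in any case, because it too uses information from after enrollment.
- **Level 2, rows:** use the follow-up histology to add a row *CIN 2 or CIN 3 first found in months 3 to 12*. Keep in the three cytology cells only women without such histology by month 12. Use a fixed month-12 cutoff, so that the cell with no or nondiagnostic cytology is also defined.
- **Where to write it:** sections 2, 5.1.2 and 6.2, and the matching Summary text.

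The cost is one extra row, a recode of data already listed in section 5.1.3, and slightly smaller cytology cells. The level-2 table will cover 51 months rather than 63, so its cumulative incidences will not be directly comparable with those at level 1; the table should say so.

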4. STUDY POPULATION

4.1 Population (base)

The study population consists of women who participated in the Dutch national cervical cancer screening program between January 2017 and December 2018. Eligible women were HPV-positive at baseline with either low-grade cytological abnormalities (ASC-US, AGC, LSIL) or stable NILM cytology one year after initial screening.

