5.1.2 Secondary study parameters/endpoints

- Time to diagnosis of cervical cancer.
- All-cause mortality.
- Type of examination at which cervical cancer diagnosis was established.
- Histological characteristics of carcinoma (subtype).
- Cervical cancer incidence in women with stable NILM cytology after one year.
- Cervical cancer incidence in women with a history of abnormal cytology or histology.
- Cervical cancer risk stratified by histological diagnosis within three months of baseline abnormal cytology (\leq CIN I vs $>$ CIN I) and, for the \leq CIN I group, further stratified by cytology at 12-month follow-up (no or nondiagnostic cytology, \leq LSIL, $>$ LSIL).

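### The 12-month ≤ LSIL level pools women who are NILM with women whose low-grade cytology persists, so no planned secondary output gives cancer incidence for either group

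*Combined protocol and SAP*

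**What the plan says.** Section 2 (Objectives) plans a secondary analysis of cancer risk "stratified by histological diagnosis within three months of baseline abnormal cytology (\leq CIN 1 vs CIN 2"+). The ≤ CIN 1 group is then "further stratified by cytology at 12-month follow-up (no or nondiagnostic cytology, \leq LSIL, HSIL"+). The Summary gives the same three levels. Section 5.1.2 writes the top level differently, "further stratified by cytology at 12-month follow-up (no or nondiagnostic cytology, \leq LSIL, $>$ LSIL"), but also has no NILM level. For these strata Section 6.2 says: "For these parameters, cumulative incidence and incidence rates will be calculated".

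Section 5.1.3 lists as collected data "Cytology according to the Bethesda system and histology results at baseline and follow-up". Outside the strata above, Section 6.3 only summarises these results as frequencies and percentages.

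The rationale concerns the course of low-grade disease. Section 1 refers to "low-grade cytological abnormalities, which often regress spontaneously without progressing to cervical cancer". The Summary takes as its comparison women with stable NILM cytology after one year, "who are currently returned to the screening program". Section 4.1 describes eligible HPV-positive women as having "either low-grade cytological abnormalities (ASC-US, AGC, LSIL) or stable NILM cytology one year after initial screening".

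**The concern.** The study is motivated by the observation that low-grade abnormalities often regress, and it asks whether follow-up can safely be reduced, with women who are NILM after one year as the comparison. Whether a low-grade abnormality has cleared or persists at 12 months is thus an obvious distinction to carry into the risk analysis. The one planned analysis that links the 12-month result to cancer merges the two groups.

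At stake is how a reader may use the ≤ LSIL row. If risk differs between the two groups, one figure is applied to both. For women whose abnormality persists, that figure may look more reassuring than it should.

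**Working it through.** **Where can a 12-month NILM result go?** The plan states no regression share, expected incidence or event count, so it has no figure of its own to reproduce. The first step is a reading of the definitions.

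1. The levels in the Summary, Section 2 and Section 5.1.2 are: no or nondiagnostic cytology; ≤ LSIL; and HSIL+ (or > LSIL).
2. NILM is a diagnostic result, so it is not in the first level. It is below LSIL, so it is not in the third. It therefore falls in ≤ LSIL. The plan does not define that label; the placement follows from the ordering and from the lack of any other level.
3. Section 6.2 plans cumulative incidence and rates for the strata as listed, with no finer split. Section 6.3 tabulates follow-up cytology without linking it to cancer.
4. The stable-NILM group does not fill the gap. Section 4.1 sets it against low-grade baseline cytology. The inclusion line in Section 4.2 omits the word stable and, read literally, could admit women with low-grade baseline cytology who are NILM at one year. They would then be mixed with women who were NILM throughout, so there would still be no separate estimate.

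**What does pooling do to the estimate?** Let r be the risk in women with NILM at 12 months, k the ratio of persistent to NILM risk, and w the share of the ≤ LSIL level that is NILM. Then:

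- pooled risk = r[w + (1 − w)k]
- pooled ÷ NILM risk = w + (1 − w)k
- pooled ÷ persistent risk = [w + (1 − w)k] ÷ k

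Both w and k are assumptions; neither is in the documents.

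| w | k | pooled ÷ NILM | pooled ÷ persistent |
|---|---|---|---|
| any | 1 | 1.0 | 1.0 |
| 0.3 | 2 | 0.3 + 0.7×2 = 1.7 | 1.7/2 = 0.85 |
| 0.7 | 2 | 0.7 + 0.3×2 = 1.3 | 1.3/2 = 0.65 |
| 0.5 | 5 | 0.5 + 0.5×5 = 3.0 | 3.0/5 = 0.60 |
| 0.3 | 10 | 0.3 + 0.7×10 = 7.3 | 7.3/10 = 0.73 |
| 0.7 | 10 | 0.7 + 0.3×10 = 3.7 | 3.7/10 = 0.37 |

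For any k above 1, the pooled risk lies above the NILM risk and below the persistent risk. At k = 1 nothing is distorted, but the planned output could not show that this is the case.

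**Would a separate row be informative?** With zero cancers among n women, the exact two-sided 95% upper limit is 1 − 0.025^(1/n). For assumed denominators of 1,000, 5,000 and 10,000 it is 0.37%, 0.07% and 0.04%. A row with no cancers can therefore still be useful if the group is large. The plan gives no denominators, so this cannot be settled in advance.

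**The case against.** The strongest reply is that the study asks something else. The primary objective is risk in the whole baseline low-grade group, and the burden described in Section 1 is that of referral for colposcopy, which depends on baseline cytology before any 12-month result exists. The stated comparison is of stable-NILM women with all low-grade women. No section names women who become NILM as the target for less follow-up. The Summary says only of women with stable NILM that they are returned to screening, not of women whose ASC-US or LSIL later became NILM. All of this stands, and it confines the point to one descriptive secondary stratification.

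A reader might also infer that the pooled figure is of no use for a follow-up decision in either group. That goes too far. If persistent women carry the higher risk, the pooled risk is an upper bound for women with NILM, so a low pooled figure is conservative for them. It also answers a coherent question: the risk when 12-month cytology is below HSIL. What survives is the narrower limit that it may understate risk in persistent women.

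Three further cautions stand:

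- The ratios above rest on assumed inputs, and a large ratio of very small risks may change no conclusion. Nor do the documents show what share of 12-month results falls in ≤ LSIL.
- NILM at 12 months is not proof of spontaneous regression. Section 4.3 has no exclusions, and the plan does not set aside women treated in between.
- A side-by-side display with the stable-NILM group could mislead without a common start. Section 2 counts these strata for five years and three months from enrollment although they are defined at 12 months, and the plan does not state where follow-up of the NILM group starts.

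**Conclusion.** The point holds as a cheap improvement to a secondary analysis. Among ≤ CIN 1 women with a diagnostic 12-month smear, the plan pools NILM with persistent low-grade cytology and gives cancer incidence for neither. That conclusion follows from the stratum definitions and needs no assumption beyond reading ≤ LSIL as including NILM.

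The direction of any distortion depends on persistent women having the higher risk, which is plausible but not stated in the documents. The size cannot be computed from them; the range of 1.3 to 7.3 times the NILM risk and 0.37 to 0.85 times the persistent risk is illustrative only.

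A reader might infer that the main result or the benchmark comparison is compromised. The documents do not support that: the primary endpoint uses the whole low-grade group, and the planned comparison with stable-NILM women does not use the 12-month strata.

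**What to change.** 1. In the Summary and Sections 2, 5.1.2 and 6.2, split the ≤ LSIL level for ≤ CIN 1 women into (a) NILM and (b) persistent low-grade cytology (ASC-US or LSIL). State where AGC at 12 months is placed; the study counts AGC as low-grade at baseline, but the strata do not mention it.
2. For each row report cases, denominator, cumulative incidence and incidence rate with exact 95% confidence intervals (Clopper-Pearson for the proportion, exact Poisson for the rate). Keep the pooled ≤ LSIL row as a total.
3. If row (a) is shown beside the stable-NILM group, count follow-up for both from the 12-month cytology and over the same length. Five years and three months from enrollment leaves four years and three months after a 12-month smear. Label the display as descriptive.
4. Reconcile Sections 4.1 and 4.2 on whether the NILM group must be stable NILM, so that no woman is counted in both groups.

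The cost is one more row in a secondary table, from data the plan already collects. The downside is fewer cancers and wider intervals in each row; the retained total keeps the planned estimate available. Specifying the split before analysis also avoids presenting it later as a post hoc subgroup.

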6. STATISTICAL ANALYSIS

6.1 Primary study parameter(s)

The primary study parameter is the incidence of histologically confirmed cervical cancer within the five-year follow-up period. The cumulative incidence will be calculated as the number of new cases diagnosed divided by the total number of women included in the cohort. The incidence rate will also be calculated as the number of cervical cancer cases divided by the total follow-up time in person-years and expressed per 1,000 person-years.

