6.3 Other study parameters

Other study parameters include baseline characteristics such as age, which will be assessed for normality using the Shapiro-Wilk test. If normally distributed, this variable will be reported as means with standard deviation (SD). If non-normally distributed, it will be reported as medians with interquartile range (IQR). Cytology and histology results at baseline and follow-up, HPV test results, and relevant medical history will be summarized as frequencies and percentages for each relevant group. For the relevant medical history, the highest histology results will be presented. In case a patient has both cytological and histological results, histology will be prioritized. Pap scores will be converted to Bethesda system classifications using the KOPAC scores.[14] Missing data will be described, and analyses will include all available data.

All statistical analyses will be conducted using SPSS Statistics version 29 (IBM Corp., Armonk, NY, USA, 2025).

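### The secondary stratified analysis sets strata at 3 and 12 months but counts follow-up from enrollment with no landmark, so smear-defined rates are understated and some early cancers are placed by their own outcome

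*Combined protocol and SAP*

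**What the plan says.** Section 5.1.2 lists as a secondary endpoint "Cervical cancer risk stratified by histological diagnosis within three months of baseline abnormal cytology". The ≤CIN 1 group is then "further stratified by cytology at 12-month follow-up (no or nondiagnostic cytology", with ≤LSIL and HSIL+ as the other two levels. Section 2 and the Summary's list of secondary endpoints give this analysis its own follow-up, "with a follow-up period of five years and three months after enrollment". Section 3 gives five years for the study as a whole. Sections 5.1.2 and 6.2 repeat the stratified analysis without a follow-up length.

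Section 6.2 covers "risk stratification by histology within three months of baseline cytology and follow-up cytology at 12 months" and adds: "For these parameters, cumulative incidence and incidence rates will be calculated". Both measures are defined in section 6.1. Cumulative incidence is "the number of new cases diagnosed divided by the total number of women included in the cohort". The rate is "the number of cervical cancer cases divided by the total follow-up time in person-years". Section 6.1 does not say when person-time starts.

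Section 4.3 has no exclusions, and section 6.3 states: "Missing data will be described, and analyses will include all available data". No section sets a landmark or delayed entry, gives a window in months around the 12-month cytology, or says where a woman belongs if cancer or death comes before her stratum can be known.

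**The concern.** Membership of a stratum is decided after the clock has started. Three consequences follow for this secondary analysis.

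(a) A cancer seen on histology by month 3 puts the woman in CIN 2+ and is also her event. The CIN 2+ versus ≤CIN 1 comparison is to that extent circular.

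(b) A ≤CIN 1 woman diagnosed between month 3 and her 12-month smear may never have a qualifying smear. She could then be coded as having no or nondiagnostic cytology, and her cancer would raise that stratum's apparent risk.

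(c) A woman who enters ≤LSIL or HSIL+ through a smear taken while cancer-free could not have had an event before it. The plan's denominator still counts those months.

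The introduction asks whether follow-up can safely be made less intensive, and the Summary hopes to inform follow-up strategies. Women with ≤CIN 1 histology and ≤LSIL at 12 months are natural candidates, and error (c) makes their rate look lower than it is. The strata are descriptive and no test is planned, but readers will still set them side by side.

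**Working it through.** **Inputs from the documents.** Follow-up of 63 months (5 years 3 months) from enrollment; histology cut-off at month 3; cytology at month 12; cases/N and cases/person-years as measures. The plan states no expected rate, sample size or bias figure, so it has no figure of its own to reproduce.

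**Assumptions.** Events are rare and follow-up is complete. Where stated, smears fall at months 9 to 15.

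**Step 1: rates in the smear-defined strata.** Let D events occur among N women after a smear at month L, with person-time counted from month o.
- Rate from the smear: D / [N(63 − L)].
- Rate with the chosen origin: D / [N(63 − o)].
- Ratio of the second to the first: (63 − L)/(63 − o). The hazard cancels.

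| Origin o | Smear month L | Ratio | Understatement |
|---|---|---|---|
| 0 | 12 | 51/63 = 0.81 | 12/63 = 19% |
| 3 | 12 | 51/60 = 0.85 | 9/60 = 15% |
| 0 | 9 | 54/63 = 0.86 | 14% |
| 0 | 15 | 48/63 = 0.76 | 24% |
| 3 | 9 | 54/60 = 0.90 | 10% |
| 3 | 15 | 48/60 = 0.80 | 20% |

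The same factor applies to ≤LSIL and to HSIL+.

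**Step 2: cumulative incidence in those strata.** D/N is the same whether counting starts at enrollment or at the smear. With a month-12 smear it covers 51 months at risk (4.25 years) but carries a 63-month label (5.25 years).

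**Step 3: contrasts.**
- ≤LSIL versus HSIL+: both carry the factor from step 1, so it largely cancels if smear timing is similar.
- ≤LSIL versus no cytology: a ≤CIN 1 woman without cytology is also free of histologically confirmed cancer to month 3, so her stratum's rate from enrollment is diluted by 60/63. The relative distortion is (51/63)/(60/63) = 51/60 = 0.85, or 15%. In cumulative incidence the same mismatch appears as 5/4.25 = 1.18.

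**Step 4: illustration of (b).** All inputs here are assumed: 10,000 ≤CIN 1 women, constant hazard h = 0.0004 per year, 12-month attendance a = 0.85, and no true association between stratum and risk. Let e = 0.75h (months 3–12), l = 4.25h (months 12–63), and p be the share of attenders' early cancers coded as no cytology, the rest going to HSIL+.
- ≤LSIL risk = l/(1 − e) = 0.0017/0.9997 = 0.170%.
- No-cytology risk = [(1 − a)(e + l) + p·a·e] / [(1 − a) + p·a·e].
- p = 0: 0.0003/0.15 = 0.200%, ratio 1.18 (the horizon mismatch alone).
- p = 0.5: 0.0004275/0.1501275 = 0.285%, ratio 1.67.
- p = 1: 0.000555/0.150255 = 0.369%, ratio 2.17.
- As p runs from 0 to 1, the ratio runs from 1.18 to 1.59 at 70% attendance and from 1.18 to 4.50 at 95%.

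Per 1,000 person-years from enrollment, ≤LSIL is 14.45/(8497.45 × 5.25) = 0.32. No cytology at p = 1 is 5.55/(1502.55 × 5.25) = 0.70. The assumed value after month 3 is 0.40 in both. The model never codes an early cancer as ≤LSIL, which the plan does not rule out. It also leaves out women without histology by month 3, for whom the plan names no stratum.

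**The case against.** The strongest reply is that the extra three months match the histology window, so the authors may intend five years counted from the point where the histology strata are set. That reading is plausible. It would soften (a) and reduce (c) to 15% for a month-12 smear. But the text says after enrollment, no section starts the count at month 3, and (b) would remain.

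A reader might infer that the ≤LSIL rate is simply 19% too low. The documents do not support that as a flat statement. It needs an enrollment origin, which section 6.1 does not give for person-time, and a smear at exactly month 12. It concerns the rate only, and it applies to HSIL+ as much as to ≤LSIL. For the comparison with no cytology the horizon effect is 15%.

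A reader might also infer that cancers in months 3 to 12 mostly end up under no cytology. Nothing in the documents shows this. With no window defined, an early smear that led to the diagnosis could place the woman in HSIL+ or ≤LSIL.

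Finally, the error may be smaller than chance variation. In the illustration ≤LSIL has about 14 events, and an exact Poisson interval for its rate is roughly 0.17 to 0.53 per 1,000 person-years, which contains both 0.32 and 0.40. That is fair for the assumed hazard. It does not excuse the error, which has a known direction, does not shrink with more data and is cheap to remove.

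**Conclusion.** The concern holds for this one secondary analysis. Followed as written, the plan builds event-free time into the ≤LSIL and HSIL+ rates and lets month 0–3 cancers act as both stratum and outcome. It would produce a wrong number; this is more than a missing detail.

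The rates in both smear-defined strata are understated by 19% or 15%, depending on the origin, for a month-12 smear, and by about 10–24% if smears fall at months 9 to 15. These figures assume rare events, complete follow-up and a smear taken while cancer-free. The effect of (b) probably runs upward for the no-cytology stratum, but its size cannot be fixed; the ratios of 1.2 to 4.5 are illustrations only.

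It would go too far to conclude that the primary five-year incidence is biased by this, that the case count per woman in ≤LSIL is wrong (only its label is), or that ≤LSIL versus HSIL+ is materially distorted by (c). The documents support none of these. The point should be fixed before analysis, in proportion to a descriptive secondary result.

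**What to change.** - Start the histology strata at month 3 and report month 0–3 cancers separately.
- Define the 12-month cytology window in months.
- For comparisons between cytology strata, start all ≤CIN 1 women who are alive and cancer-free at one common landmark, the end of that window. Count events and person-years from there to 5 years 3 months after enrollment, and label the horizon.
- Tabulate cancers and deaths before the landmark in separate rows, with smear-triggered cancers shown by smear result.
- Rates from the smear date may be added as a within-stratum description of ≤LSIL and HSIL+, but not for the contrast with no cytology.
- Leave the primary endpoint and its five-year window unchanged.

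The landmark must be common. Suppose smear-date starts average month 12 and women without cytology start at month 15. With an assumed hazard half-life of 12 months, the no-cytology/≤LSIL ratio would be about 2^(−3/12) = 0.84 with no true association. At a 24-month half-life it would be 2^(−3/24) = 0.92. Such unequal starts would create an error about as large as the one being removed.

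The cost is wording, recoded start dates in existing data, and fewer events in the cytology strata. In the illustration, 10,000 × 0.0004 × 5 = 20 cancers occur from month 3 to month 63. A month-15 landmark moves 10,000 × 0.0004 × 1 = 4 of them (20%) to the separate rows; a month-12 landmark moves 3 (15%). All are still reported. With a month-15 landmark and the constant hazard, both strata then show 0.40 per 1,000 person-years and 0.16% over four years. That equality belongs to the illustration and should not be promised for the real data.
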